5.2 Exclusion criteria

Patients eligible for participation in this study must not meet any of the following criteria:

1. Patients overexpressing HER2 by local laboratory testing (IHC 3+ staining or in situ hybridization positive), based on the most recent test. Patients with IHC 2+ must have a negative in situ hybridization test.
2. Patients with only non-measurable lesions other than bone metastasis (e.g. pleural effusion, ascites).
3. Patients with more than one prior chemotherapy line for treating metastatic breast cancer. A chemotherapy line is an anticancer regimen(s) that contains at least 1 cytotoxic chemotherapy agent, given for a minimum of 21 days. A cytotoxic chemotherapy regimen that lasted less than 21 days and was discontinued for a reason other than disease progression is not accounted as a "prior line of chemotherapy".
4. Previous treatment with mTOR inhibitors.
5. Known hypersensitivity to mTOR inhibitors, e.g. Sirolimus (rapamycin).
6. Any other malignancy within 5 years prior to enrolment, with the exception of adequately treated in-situ carcinoma of the cervix uteri, basal or squamous skin cell carcinoma, or non-melanoma skin cancer.
7. Radiotherapy within four weeks prior to enrolment, except radiotherapy to the bone for analgesic purpose or for lytic lesions at risk of fracture. Patients must have recovered from radiotherapy toxicities prior to enrolment.
8. Patient receiving hormone replacement therapy (HRT). Patient may be enrolled after discontinuation of HRT.
9. History of brain or other CNS metastases, including leptomeningeal metastasis.

10. Treatment with immunosuppressive agents or chronic corticosteroids, with the following exceptions:
 - Patients on stable low dose of systemic corticosteroids for at least two weeks before enrolment
 - Corticosteroids used in topical applications (e.g. cream), inhaled sprays, eye drops or local (e.g. intra-articular) injections.
11. Bilateral diffuse lymphangitic carcinomatosis.
12. Patients with a known history of HIV seropositivity. Screening for HIV infection at baseline is not required.
13. Active, bleeding diathesis. Patients treated with anti-vitamin K medication, LMWH, or anti-platelet medication must have an INR ≤ 2.0 .
14. Any severe and / or uncontrolled medical conditions such as:
 - a. Unstable angina pectoris, symptomatic congestive heart failure, myocardial infarction ≤ 6 months prior to enrolment, serious uncontrolled cardiac arrhythmia
 - b. Uncontrolled diabetes as defined by fasting serum glucose $> 1.5 \times$ ULN
 - c. Acute and chronic, active infectious disorders (except for Hep B and Hep C positive patients) and non-malignant medical illnesses that are uncontrolled or whose control may be jeopardized by the complications of this study therapy
 - d. Impairment of gastrointestinal function or who have gastrointestinal disease that may significantly alter the absorption of study drugs (e.g., ulcerative disease, uncontrolled nausea, vomiting, diarrhea, malabsorption syndrome)
 - e. Active skin, mucosa, ocular or gastro-intestinal disorders of Grade > 1
 - f. Significant symptomatic deterioration of lung function. If clinically indicated, pulmonary function tests including measures of predicted lung volumes, DLco, O2 saturation at rest on room air should be considered to exclude restrictive pulmonary disease, pneumonitis or pulmonary infiltrates.
15. Patients being treated with drugs recognized as being strong inhibitors or inducers of the isoenzyme CYP3A at enrolment (rifabutin, rifampicin, clarithromycin, ketoconazole, itraconazole, letrozole, voriconazole, ritonavir, telithromycin) continuously for at least 7 days during any time period in the last 2 weeks prior to enrolment (clinically relevant drug interaction are listed in [Section 6.4.1](#)).
16. Patients unwilling to or unable to comply with the protocol.
17. Patients enrolled in another investigational drug or device study.
18. Patients who have discontinued this study may not be re-enrolled.

6 Treatments

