5.1 Inclusion criteria

Patients eligible for inclusion in this study have to meet all of the following criteria:

1. Adult women (≥ 18 years of age) with metastatic, recurrent or locally advanced breast cancer not amenable to curative treatment by surgery or radiotherapy.
2. Histological or cytological confirmation of hormone receptor positive (HR+) breast cancer.
3. Postmenopausal women. Ovarian radiation or treatment with a luteinizing hormone-releasing hormone (LHRH) agonist (goserelin acetate or leuprolide acetate) does not satisfy this inclusion criterion. Postmenopausal status is defined by one of the following:
 - Age ≥ 55 years and one year or more of amenorrhea
 - Age < 55 years and one year or more of amenorrhea, with estradiol assay < 20 pg/ml and/or post-menopausal levels of FSH and LH per local institutional standards

- Prior hysterectomy, with estradiol assay < 20 pg/ml and/or post-menopausal levels of FSH and LH per local institutional standards
 - Surgical menopause with bilateral oophorectomy.
4. Disease refractory to non-steroidal aromatase inhibitors (NSAI), defined as:
- Recurrence while on, or within 12 months (365 days) of completion of adjuvant therapy with letrozole or anastrozole,
or
 - Progression while on, or within one month (30 days) of completion of letrozole or anastrozole treatment for ABC.
 - Notes: Letrozole or anastrozole do not have to be the last treatment prior to study baseline. Patients may have received one prior chemotherapy line for ABC, or have received other endocrine treatments such as tamoxifen, or fulvestrant and including exemestane monotherapy.
5. Radiological or objective evidence of recurrence or progression on or after the last systemic therapy prior to enrolment.
- Notes: The last line of therapy may be any other treatment than mTOR inhibitors. Patients must have recovered to grade 1 or better from any adverse events related to previous therapy (except alopecia) prior to enrolment.
6. Patients must have:
- Measurable disease defined as at least one lesion that can be accurately measured in at least one dimension ≥ 20 mm with conventional imaging techniques or ≥ 10 mm with spiral CT or MRI,
or
 - Bone lesions: lytic or mixed (lytic + blastic) in the absence of measurable disease as defined above.
- Note: Lymph nodes must be ≥ 15 mm in the short axis to be considered measurable
Patients with bone lesions and at least one measurable lesion are considered as having measurable disease

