6.4.1 Prohibited concomitant therapy

Local radiotherapy for analgesic purpose or for lytic lesions at risk of fracture should have been completed two weeks prior to enrolment. Patients must have recovered from radiotherapy toxicities prior to enrolment in the study.

Everolimus may affect the response to vaccinations making it less effective. Live vaccines must be avoided during treatment with everolimus. Examples of live vaccines are: intranasal influenza, measles, mumps, rubella, oral polio, BCG (Bacillus Calmette-Guérin), yellow fever, varicella, and TY21a typhoid vaccines.

Administration of the following treatments is prohibited during the study period:

- Investigational or commercial anticancer agents, such as chemotherapy, immunotherapy, targeted therapy, biological response modifiers, or endocrine therapy other than exemestane (including steroids)
- Hormone replacement therapy, topical estrogens (including any intra-vaginal preparations), megestrol acetate and selective estrogen-receptor modulators (e.g. raloxifene).

Treatment with topical applications (e.g. rash), inhaled sprays (e.g. obstructive airways diseases), eye drops or local injections (e.g. intra-articular) of corticosteroids is allowed. Chronic low dose therapy with systemic corticosteroids, i.e. ≤ 10 mg/day prednisolone equivalent, is also allowed.

Hematopoietic growth factors (e.g. erythropoietin, G-CSF and GM-CSF) are not to be administered prophylactically. Their use must be reserved to cases of Grade 3 or 4 neutropenia and anemia as per the labeling of these agents.

Where possible, it is recommended to avoid drugs or substances known to be inhibitors or inducers of the isoenzyme CYP3A as systemic therapy in association with everolimus as these can alter its metabolism:

- Co-administration of everolimus with strong CYP3A inhibitors (e.g. ketoconazole, itraconazole, ritonavir, clarithromycin and telithromycin), and strong inducers (e.g. rifampin, rifabutin) should be avoided.
- Co-administration of everolimus with moderate CYP3A inhibitors (e.g. erythromycin, fluconazole, calcium channel blockers, benzodiazepines, verapamil, diltiazem, amprenavir, fosamprenavir or aprepitant) and PgP inhibitors should also be used with caution (e.g. increased frequency of safety monitoring).
- Co-administration of everolimus with strong CYP3A4 inducers (e.g. phenytoin, carbamazepin, rifampin, rifabutin, Phenobarbital, St John's wort) should be avoided.

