- Sevilla orange, grapefruit and grapefruit juice affect cytochrome P450 and PgP activity and must therefore be avoided during study drug intake.

Clinically relevant inducers, inhibitors and substrates of CYP3A and PgP are listed in [Table 6-8](#) and [Table 6-9](#).

Table 6-8 Clinically relevant drug interactions: inducers, and inhibitors of isoenzyme CYP3A

Inducers

Strong inducers:

avasimibe, carbamazepine, mitotane, phenobarbital, phenytoin, rifabutin, rifampin (rifampicin), St. John's wort

(hypericum perforatum)

Moderate inducers:

bosentan, efavirenz, etravirine, genistein, modafinil, nafcillin, ritonavir, [talviraline], thioridazine, tipranavir

Weak inducers:

amprenavir, aprepitant, armodafinil (R-modafinil), bexarotene, clobazam, danshen, dexamethasone, Echinacea,

garlic (allium sativum), ginkgo (ginkgo biloba), glycyrrhizin, methylprednisolone, nevirapine, oxcarbazepine,

pioglitazone, prednisone, [pleconaril], primidone, raltegravir, rufinamide, sorafenib, telaprevir, terbinafine,

topiramate, [troglitazone] , vinblastine

Inhibitors

Strong inhibitors:

boceprevir, clarithromycin, cobicistat, conivaptan, elvitegravir, indinavir, itraconazole, ketoconazole, lopinavir,

mibefradil, nefazodone, nelfinavir, posaconazole (Krishna et al 2009), ritonavir, saquinavir, telaprevir, telithromycin, tipranavir, troleandomycin, voriconazole

Moderate inhibitors:

Amprenavir, aprepitant, atazanavir, casopitant, cimetidine, ciprofloxacin, cyclosporine, darunavir, diltiazem,

dronedarone, erythromycin, fluconazole, fosamprenavir, grapefruit juice (citrus parasidi fruit juice), imatinib,

schisandra sphenanthera, tofisopam, verapamil

Table 6-9 Clinically relevant drug interactions: substrates, inducers, inhibitors of PgP and PgP/CYP3A dual inhibitors

Substrates
colchicine, digoxin, fexofenadine, indinavir, paclitaxel, talinolol, topotecan, vincristine, everolimus
Inducers
rifampin, St John's wort
PgP Inhibitors and PgP/CYP3A Dual Inhibitors

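### Exclusion 15 names letrozole as a strong CYP3A drug although the section it cites does not list it; SAP Table 1.6 reverses the consent-date deviation, and Listing 3 label E4 is out of date

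*Protocol*

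**What the plan says.** **Letrozole.** Protocol Section 5.2, item 15, opens with "Patients being treated with drugs recognized as being strong inhibitors or inducers of the isoenzyme CYP3A at enrolment". It then names nine drugs and closes with "itraconazole, letrozole, voriconazole, ritonavir, telithromycin) continuously for at least 7 days during any time period in the last 2 weeks prior to enrolment", referring the reader to Section 6.4.1.

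The text of Section 6.4.1 addresses "strong CYP3A inhibitors (e.g. ketoconazole, itraconazole, ritonavir, clarithromycin and telithromycin), and strong inducers (e.g. rifampin, rifabutin) should be avoided". Table 6-8 gives the fuller lists. Strong inhibitors include "boceprevir, clarithromycin, cobicistat, conivaptan, elvitegravir, indinavir, itraconazole, ketoconazole, lopinavir" and "ritonavir, saquinavir, telaprevir, telithromycin, tipranavir, troleandomycin, voriconazole"; strong inducers include "avasimibe, carbamazepine, mitotane, phenobarbital, phenytoin, rifabutin, rifampin (rifampicin". Letrozole is not among them. The same section bars, during the study, anticancer agents "or endocrine therapy other than exemestane (including steroids".

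Inclusion 4 (Section 5.1) makes letrozole one of the two qualifying aromatase inhibitors: "Progression while on, or within one month (30 days) of completion of letrozole or anastrozole treatment for ABC". Section 5 leaves the last anticancer treatment open apart from mTOR inhibitors. SAP Table 2.1.3 has a row for patients whose most recent treatment was anastrozole or letrozole.

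**Consent date.** Protocol Sections 4.1 and 5, and inclusion 14, require consent before any study procedure. SAP Table 1.6 has a major-deviation row for a consent form dated earlier than the first visit or procedure.

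**Prior exemestane.** Exclusion 4 (Section 5.2) names mTOR inhibitors only, and the notes to inclusion 4 accept earlier exemestane monotherapy. The footnote to SAP Listing 3 still defines E4 as prior exemestane or mTOR inhibitors.

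**The concern.** Exclusion 15 is a rule that sites must apply. Section 12 of the protocol allows no authorised deviations, and Section 9.2 requires full verification of eligibility. A site following the text literally would hold back a patient who has just come off letrozole, while a comparable patient coming off anastrozole enters at once. A site that enrols her anyway may generate an exclusion-criterion violation in SAP Table 1.6.

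The two SAP items affect reporting. If the consent row is programmed as worded, it counts compliant patients as major deviators and misses the fault it was presumably meant to find. The E4 label makes an allowed prior therapy look like a breach in the eligibility listing. If the same rules feed the Per-Protocol Set, eligible patients could drop out of the supportive efficacy analysis.

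**Working it through.** **1. Exclusion 15 against Section 6.4.1, drug by drug**

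| Named in exclusion 15 | Class in Table 6-8 |
|---|---|
| rifabutin, rifampicin | strong inducer |
| clarithromycin, ketoconazole, itraconazole, voriconazole, ritonavir, telithromycin | strong inhibitor |
| letrozole | none; also absent from the Section 6.4.1 text and Table 6-9 |

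Count: 2 + 6 = 8 of 9 are confirmed as strong, and letrozole is the one left over. Table 6-8 has no class of weak inhibitors, so its silence says nothing about weak inhibition. Exclusion 15, however, presents letrozole as strong.

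**2. What the time window does**

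Suppose letrozole was taken daily and stopped *d* days before enrolment. The last 14 days then contain 14 − *d* continuous days of use.

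- Wider reading (7 or more continuous days anywhere in the window): excluded if 14 − *d* ≥ 7, that is *d* ≤ 7. At *d* = 7, 14 − 7 = 7, excluded. At *d* = 8, 14 − 8 = 6, not excluded. The wait still to run is 8 − *d* days, from 8 (just stopped) down to 1.
- Narrower reading (must also be on the drug at enrolment): only *d* = 0 is excluded. The ban in Section 6.4.1 on endocrine therapy other than exemestane already rules out continuing letrozole on study.

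A wait of 8 days fits within the 21-day screening period of Section 4.1 if letrozole stops early enough in it. It does not cost the patient her qualification under inclusion 4, because the 30-day and 12-month limits there run from the end of the aromatase inhibitor to progression or recurrence, not to enrolment.

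**3. The consent row in SAP Table 1.6**

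| Consent date relative to first visit or procedure | Protocol | Row as worded | Row reversed |
|---|---|---|---|
| Earlier date | compliant | counted | not counted |
| Same date | cannot be judged from dates alone | not counted | not counted |
| Later date | breach | missed | counted |

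Late consent may still be caught through inclusion 14 in the inclusion-criteria row of the same table.

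**4. Label E4**

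The Amendment 1 rationale gives 114 patients enrolled by 18 November 2013, and the Amendment 2 rationale gives 198 by 30 June 2014: 198 − 114 = 84 enrolled in between. Amendment 1 removed the exemestane exclusion, so the old label fits the first 114. The date the amendment took effect is not given, so the 84 cannot be divided between old and current criteria.

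**The case against.** Several counter-arguments have force.

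- *Letrozole.* Inclusion 4 describes when the disease progressed and does not require letrozole to be the last or current treatment, so there is no standing clash with it. The drugs in the Section 6.4.1 text are only examples. Recruitment ends by 31 October 2014 at the latest, so few entrants may be affected. All of this stands. What remains is Table 6-8, which is not framed as examples, and an eligibility criterion that cites it for a drug it does not contain.
- *Consent row.* The SAP supplied consists of output shells, and Section 10.1 of the protocol places the Per-Protocol deviation criteria in planning documentation that was not supplied. The program behind the row may therefore be right. That is fair, but the printed label would then state the opposite of what was counted.
- *E4.* The label is partly a version effect and is correct for patients enrolled under the earlier criterion. This stands, and it is why the remedy is to show the label by version.

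A reader might also infer that the ER-positive wording of label I2 misclassifies ER-negative, PgR-positive patients. The documents do not support that. The receptor row in Table 1.6 is already worded in terms of hormone receptor status, Table 2.1.2 and Listing 26 report the two receptors separately, and Subgroup 4 reports these patients as a group. Label I2, the reference to randomization in E7, the glossary definition of enrolment and the leftover ER-positive wording in the protocol title, summary and Section 10.5 are editorial.

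**Conclusion.** The point holds in a limited form. Three texts are wrong or unreconciled as written: letrozole in exclusion 15, the consent-date row in SAP Table 1.6, and label E4 in SAP Listing 3.

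The effect is confined to timing of entry, deviation counts, listings and possibly the Per-Protocol Set, which Section 10.6.1 treats as supportive. For letrozole, the size is a delay of at most about 8 days on the wider reading, assuming daily use up to stopping and counting in whole days. On the narrower reading nothing is added beyond the on-study ban. The documents do not say how many patients had recent letrozole, so neither a patient count nor a loss of precision can be given.

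A reader might infer that exclusion 15 shuts out the trial's own target population, or that the safety or efficacy results are biased. The first does not follow, because the restriction ends within days of stopping letrozole. The second does not follow, because the Safety Set and Full Analysis Set are defined by dosing (and, for safety, a post-baseline assessment), not by eligibility deviations. Whether letrozole belongs in the list is not decided here.

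**What to change.** 1. The sponsor should reconcile exclusion 15 with Section 6.4.1 and Table 6-8, inclusion 4 and Section 5, and state which reading of the time window applies.
2. For patients already enrolled, classify deviations by the protocol version in force at their enrolment and flag recent letrozole use separately. Judging them by text reconciled later would apply a rule that did not exist when they entered.
3. Reverse the consent row in SAP Table 1.6 so that it counts a consent date later than the first visit or procedure.
4. Show the E4 label in SAP Listing 3 by protocol version.
5. In the same pass, align I2, E7, the glossary entry for enrolment and the remaining ER-positive wording with the current criteria.

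The cost is one eligibility clarification, one row label, one label split by version and a few editorial corrections. The SAP changes should be made before database lock. No new data collection is needed if the recorded prior-therapy end dates are used to flag recent letrozole.

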6.1 Study treatments

This is a non-randomized, single-arm, open-label study. The investigational drugs used in the course of this trial are everolimus in combination with exemestane. All patients will be assigned to treatment with everolimus and exemestane.

6.1.1 Everolimus

Everolimus is formulated as tablets of 10 and 5 mg strength for oral administration. The dose is 10 mg once daily (as one tablet of 10 mg or two tablets of 5 mg at a time) per oral route.

6.1.2 Exemestane

Commercially available exemestane will be supplied as tablets of 25 mg strength for oral administration. The dose is 25 mg once daily (one tablet) per oral route.

Complete guidelines for management and administration of exemestane can be found in the package insert.

6.1.3 Dosing regimen

All patients will receive everolimus + exemestane. All patients will take everolimus 10 mg orally per day. All patients will also take one 25 mg tablet of exemestane once daily (Table 6-1).

Table 6-1 Starting dose and treatment schedule

Study drugs	Pharmaceutical form, route of administration	Dose	Frequency
Everolimus (RAD0001)	Tablets for oral use	1 tablet of 10 mg or 2 tablets of 5 mg*	Daily
Exemestane	Tablets for oral use	25 mg	Daily

*: Choice will be made at each participating country level

Patients will be provided with study treatment for self administration at home, starting on Treatment Day 1. Enough tablets should be provided to cover administration until next scheduled visit.

[figure not shown]
Everolimus and exemestane will be dosed starting on Treatment Day 1 (Visit 2).

Patients will be instructed to take one 10 mg tablet of everolimus or 2 tablets of 5 mg at a time per oral route with a large glass of water at the same time every day with or without food. The tablets should not be chewed or crushed.

Similarly, patients will be instructed to take one 25 mg tablet of exemestane orally with a large glass of water at the same time every day. Package insert instructions should be followed.

Everolimus should be swallowed whole with a glass of water and the tablets should not be chewed or crushed and grapefruit or citrus juices must be avoided for everolimus administration. If the tablets cannot be swallowed, the tablets should be disintegrated in approximately 30 ml of water. Immediately prior to administration, the contents should be stirred gently until the tablets have disintegrated into a suspension. The patient should then drink the contents. Afterwards, the glass should be rinsed with an additional 30 ml of liquid and drunk by the patient. If vomiting occurs no attempt should be made to replace the dose.

Everolimus and exemestane will be taken daily from Visit 2, Day 1 until disease progression, unacceptable toxicity, death, and withdrawal from the study for any other reason.

The End of Treatment (EOT) is defined as the last date that the patient has taken the study drug everolimus, excluding an everolimus interruption for < 4 weeks. A Follow-up visit 30 days (\pm 2 days) after the last date that the patient has taken the study drug will be conducted to report any adverse events during this period.

The investigator should promote compliance by instructing the patient to take the study drugs exactly as prescribed and by stating that compliance is necessary for the patient's safety and the validity of the study. The patient should be instructed to contact the investigator if she is unable for any reason to take the study drug as prescribed.

All dosages prescribed and dispensed to the patient and all dose changes during the study must be recorded on the Dosage Administration Record CRF.

6.1.4 Treatment duration

Patients will be treated with everolimus and exemestane until progression of disease, unacceptable toxicity, death, consent withdrawal, or discontinuation for any other reason.

